## **1. ABBREVIATIONS AND DEFINITIONS**

#### **1.1 Abbreviations**

**AE** = Adverse event **CHF** = Congestive heart failure **ED** = Emergency Department **GCS** = Glasgow Coma Scale HIPAA = Health Insurance Portability and Accountability Act **IRB** = Institutional Review Board **ICU** = Intensive Care Unit ICD-9-CM = International Classification of Disease, version 9, clinical modification ICD-10-CM = International Classification of Disease, version 10, clinical modification **INR** = International normalized ratio **ISM** = Independent safety monitor **ITT** = Intent to treat **MAP** = Mean arterial pressure **NIH** = National Institutes of Health **PE** = Pulmonary embolism **PI** = Principle investigator **PHI** = Protected Health Information **REDCap** = Research Electronic Data Capture **RR** = Respiratory rate **SOFA score** = Sequential Organ Failure Assessment score **SBP** = Systolic blood pressure **SpO2** = Oxygen saturation via pulse oximetry **SUSAR =** Serious and Unexpected Suspected Adverse Reactions **SAEs=** Serious Adverse Events

**WBC** = White blood cell count

#### **1.2 Definitions**

- Adverse Event: Any untoward medical occurrence associated with the use of a drug or a study procedure, whether or not considered drug related.
- Adverse reaction: An adverse reaction means any adverse event caused by a study intervention. An adverse reaction is a subset of all suspected adverse reactions where there is a reason to conclude that the study intervention caused the event.
- **Door-to-antibiotic time**: Primary outcome; the time from the first recorded arrival time in ED (usually ED triage or registration) and the time the first eligible antibiotic was administered.
- **Hypotension**: SBP <90 mmHg or MAP <65 mmHg or, where applicable, receipt of vasopressor medication
- Intention to Treat (ITT): All eligible patients who present to the ED will be included in the ITT cohort for the purposes of analyzing the primary and secondary study outcomes.
- **PHI:** identifiable health information that is used, maintained, stored, or transmitted by a HIPAA-covered entity
- **SAEs:** Serious Adverse Events Adverse events that are serious and unexpected and have a reasonable possibility that the event was due to a study procedure
- Sepsis: Life-threatening organ dysfunction resulting from a dysregulated host response to infection, clinically identified in the emergency department (ED) by an acute rise in the Sequential Organ Failure Assessment (SOFA) score while in the ED ≥2 points above baseline plus suspected or confirmed infection in the ED.1
- Sepsis mimic: Clinical condition which may cause patient to exhibit and/or be treated for sepsis even though infection is not actually present. For the present study, pulmonary embolism (PE) and congestive heart failure (CHF) have been identified as sepsis mimic conditions.
- Septic shock: Sepsis associated with hypotension requiring administration of vasopressors.
- Study hospital: Defined as the hospital where the patient presented to the ED.
- **Suspected adverse reaction**: any adverse event for which there is a reasonable possibility that the study procedures caused the adverse event. Reasonable possibility means there is evidence to suggest a causal relationship between the study procedures and the adverse event. A suspected adverse reaction implies a lesser degree of certainty about causality than adverse reaction (21 CFR 312.32(a)).
- Suspected or confirmed infection in the emergency department: Identified based on clinical behaviors of clinicians as the combination of administration of an IV- or IV-equivalent antibiotic plus collection of a body fluid culture or a positive molecular test for infection.
- Suspected Unexpected Serious Adverse Reaction (SUSAR) An adverse reaction that is both unexpected (not consistent with the risks outlined in the protocol or investigator brochure), serious, and meets the definition of a Suspected Adverse Reaction

### 2. STUDY SUMMARY

#### 2.1 Title

Effects of Code Sepsis Implementation on ED Sepsis Care (Code Sepsis)

#### 2.2 Primary Objective

Determine the effects of reorganizing ED sepsis care (Code Sepsis protocol) on door-to-antibiotic time for ED patients with sepsis.

#### 2.3 Primary Hypothesis

Early activation of a multidisciplinary, coordinated, team-based assessment and treatment protocol for patients with potential sepsis will decrease door-to-antibiotic time for ED patients with sepsis.

#### 2.4 Study Design

Pragmatic phase 2a pre/post single-center implementation study with contemporaneous controls testing reorganization of standard ED sepsis care around a protocol for early, coordinated, multidisciplinary protocol for assessment of patients with potential sepsis (Code Sepsis protocol).

- 1. We will emphasize pragmatic, real-world implementation of the Code Sepsis protocol in a single ED.
- 2. We will compare care delivered to ED patients after Code Sepsis protocol implementation in the intervention ED to care received in this ED prior to Code Sepsis implementation.
- 3. We will conduct a quasi-experimental analysis using contemporaneous control data obtained from two non-intervention hospitals to control for temporal trends in studied outcomes not resulting from the tested intervention.
- 4. We will measure the effects of protocol implementation on all ED patients with sepsis (including patients not treated under the Code Sepsis protocol) as well as potential bystander effects.

#### 2.4.1 Study groups and phases

Phase #1: Pre intervention (November 13, 2018 to November 12, 2019)

- Control EDs: Standard care
- Intervention ED: Standard care
- *Phase #2*: Intervention roll-in (November 13, 2019 to February 12, 2020)
  - Control EDs: Standard care
  - Intervention ED: Launch and fine-tuning of Code Sepsis protocol, fine tuning of Code Sepsis activation mechanism.

*Phase #3*: Full intervention (February 13, 2020 to February 12, 2021)

- Control EDs: Standard care
- Intervention ED: Full implementation of Code Sepsis protocol

#### 2.4.2 Inclusion criteria

- 1. Age ≥18 years
- 2. Arrival to intervention or a control ED during study period

#### 2.4.3 Exclusion criteria

1. Age <18 years

2. Trauma patient

#### 2.4.5 Primary analysis cohort

ED patients with clinical sepsis, as identified by the combination of

- 1) Acute organ failure: SOFA score while in the ED  $\ge$ 2 points above baseline
- 2) Suspected or confirmed infection while in the ED, as identified by both:
  - a) Administration of ≥1 IV or IV-equivalent antibiotics while in the ED
  - b) Collection of  $\geq 1$  body fluid cultures while in the ED

#### 2.4.6 Primary outcome

Door-to-antibiotic time

#### 2.4.7 Secondary outcomes

- Mortality (including 30-day, 1-year, hospital)
- Hospital charges
- Hospital length of stay
- Code Sepsis activation rate
- Code Sepsis activation accuracy
- Antibiotic utilization fraction
- Antibiotic spectrum
- Antibiotic overtreatment rate
- Adverse drug & allergic reaction incidence (e.g. anaphylaxis, new onset *Clostridium difficile* infection)

#### 2.4.8 Data analysis

The primary analysis will use quasi-experimental methods to compare sepsis patients' adjusted mean door-to-antibiotic time (primary outcome) at the intervention hospital pre- versus post-implementation of the Code Sepsis protocol using the measured change at non-intervention hospitals to control for pre- versus post-intervention changes not attributable to protocol implementation. Secondary analyses will compare the change in secondary outcomes using similar methods.

#### 2.4.9 Sample size

Assuming 4.5 sepsis patients per day at the intervention ED, treatment of 30% of these patients by Code Sepsis teams during study phase #3, and 6 total sepsis patients daily in control EDs (all conservative estimates), I will have 90% power to detect a change ≥16 minutes in the overall average door-to-antibiotic time among all ED sepsis patients after Code Sepsis implementation at the intervention hospital.

## 3. TRIAL DESCRIPTION

#### 3.1 Background

Sepsis, the combination of infection and acute organ dysfunction, is a common, morbid, and often lethal syndrome. Sepsis hospitalizes 1.3 million patients each year, kills 20%, and costs \$23.7 billion. Early, appropriate antibiotic initiation is critical: sepsis survival decreases with every hour's delay.  While guidelines and government mandates thus emphasize prompt antibiotics, international guidelines' have admitted a lack of data to support the feasibility or implementation of their one-hour door-to-antibiotic goal.

Among patients presenting to the emergency department (ED) with sepsis, we previously found that non-patient contextual cues could improve rapid antibiotic initiation, whereas ED busyness was associated with delayed antibiotics. I also discovered five-fold variation between physicians in median door-to-antibiotic time. ED care reorganization could bypass these cognitive, stylistic, and resource barriers to timely sepsis treatment. In fact, ED protocols linking prehospital notification to a multidisciplinary, team-based response are common and effective for trauma, stroke, and myocardial infarction, conditions that are less common and less mortal than sepsis but require similarly time-sensitive treatment. Given that sepsis has a less definitive presentation, however, analogous protocols for sepsis could waste resources or promote anchoring bias and overtreatment of patients without sepsis, issues observed with door-to-antibiotic standards for pneumonia.

We hypothesize that reorganizing ED sepsis care around multidisciplinary "Code Sepsis" teams activated prior to or upon patients' ED arrival will reduce door-to-antibiotic times — with tolerable overtreatment rates — by mobilizing personnel, systematizing illness severity and infection risk assessment, facilitating test completion, and eliminating any gap between treatment decision and antibiotic infusion. This study will therefore evaluate the effectiveness and tradeoffs of a Code Sepsis program for ED sepsis patients.

#### 3.2 Overall Study Motivation, Aim and Hypothesis

Many emergency department (ED) patients with sepsis do not receive antibiotics and other care within intervals recommended in international guidelines. Efforts to accelerate treatment, however, may lead to overtreatment and other adverse effects. The goal of this project is to determine the potential effectiveness and tradeoffs of a Code Sepsis program for ED sepsis patients.

Aim: Establish the feasibility and effects of a team-based Code Sepsis protocol designed to accelerate antibiotic initiation for ED patients with suspected sepsis.

Using preexisting infrastructure, implement prehospital- or triage-activated Code Sepsis ED teams in a single ED and compare sepsis patients' door-to-antibiotic times pre- and post-implementation, controlling for unrelated temporal trends with observational data from two non-intervention EDs.

Hypothesis: Prehospital or triage-based activation of an ED team prepared to rapidly diagnose and treat sepsis decreases door-to-antibiotic time without increasing overtreatment.

#### 3.3 Primary Objective

Determine the effect of reorganizing ED sepsis care (Code Sepsis protocol) on door-to-antibiotic time for ED patients with sepsis.

#### **3.4 Primary Hypothesis**

Early activation of a multidisciplinary, coordinated, team-based assessment and treatment protocol for patients with potential sepsis will decrease door-to-antibiotic times for ED patients with sepsis.

#### 3.5 Study Overview

To assess feasibility and test the preliminary efficacy of ED-based Code Sepsis teams activated on or before patients' ED arrival, we will pursue a Phase 2a implementation trial involving Code Sepsis team activation in one ED (Intermountain Medical Center [IMC]) while collecting contemporaneous control data at two other urban EDs (Utah Valley Hospital and Dixie Regional Medical Center [control sites], Table 1).

Months 1-12: Collect baseline data (all sites), refine Code Sepsis protocol, and train ED staff at IMC.

Portions of baseline data may be collected in a retrospective fashion. At the intervention site during this period, we may also undertake preparatory work to Code Sepsis protocol launch, including anonymous patient care observations to evaluate care processes; pilot testing of the draft Code Sepsis protocol or its components; and testing of the

Figure 1. Code Sepsis implementation and data collection for Aim III.

accuracy of Code Sepsis activation mechanisms.

• Months 13-15: Run-in period: implement Code Sepsis protocol at IMC, optimize protocol & its trigger.

 Months 25-36: Continue Code Sepsis protocol at site A (intervention ED). Continue standard care processes for sepsis without change (control condition) at two non-intervention EDs Using contemporaneous controls and rigorous statistical methods, we will assess how implementation of the Code Sepsis protocol affects process and patient outcomes in the intervention ED (Figure 1). Continuation of the Code Sepsis protocol (with or without revision) by the intervention ED and/or adoption elsewhere within the Intermountain Healthcare system is expected to be contingent on the results of these analyses.

#### 3.6 Analysis cohorts

#### 3.6.1 Primary analysis cohort

ED patients with clinical sepsis, as identified by the combination of

- 1) Acute organ failure: SOFA score while in the ED  $\ge$ 2 points above baseline
- 2) Suspected or confirmed infection while in the ED, as identified by both:
  - c) Administration of ≥1 IV or IV-equivalent antibiotics while in the ED (see Appendix A)
  - d) Collection of  $\geq$ 1 body fluid cultures while in the ED

#### 3.6.2 Secondary and sensitivity analysis cohorts

#### 1) All eligible ED patients

- 2) ED patients with a "sepsis mimic" diagnosis based on a primary ICD-10 discharge diagnosis codes for congestive heart failure or venous thromboembolism with no diagnostic code for infection (see Appendix B).
- "Likely" sepsis patients based on simple triage assessment to include fever and at least 1 out of 3 of hypotension (SBP <90 mmHg), altered mental status (GCS ≤14), or respiratory failure (RR ≥22 or SpO2 ≤85%).

#### 3.6.3 Subgroups

A priori subgroups will include: sex; hypotension (SBP <90 mmHg or MAP <65 mmHg) present on ED arrival.

#### 3.7 Endpoints

Analysis will be conducted on an intention to treat basis.

#### 3.7.1 Primary outcome

Door-to-antibiotic time among all ED sepsis patients. Door-to-antibiotic time is the time from the first recorded arrival time in ED (usually ED triage or registration) and the time the first eligible antibiotic was administered (Appendix A).

#### 3.7.2 Secondary outcomes

- Clinical/patient-centered secondary outcomes (measured among all ED sepsis patients):
  - 1) All-cause mortality to day 30
  - 2) All-cause mortality to 1 year
  - 3) In-hospital all-cause mortality
  - 4) Hospital charges: Amount charged to patient for their medical care during index ED visit and associated hospitalization.
  - 5) Hospital length of stay
- Process/feasibility secondary outcomes
  - 1) Code Sepsis activation rate: Measured as the percentage of all ED patients for whom the Code Sepsis protocol was activated.
  - 2) Code Sepsis activation accuracy metrics. Accurate Code Sepsis activation is defined as activation for patients who have sepsis while in the ED and no activation for patients who do not have sepsis in the ED.
- Adverse effects and unintended outcomes of protocol implementation

- 1) Antibiotic utilization percentage: measured as the fraction of (1) all ED patients; (2) Code Sepsis activation patients; or (3) "likely" sepsis patients who received IV or IV-equivalent antibiotics.
- 2) Antibiotic spectrum: Total Stenehjem antibiotic spectrum score for all antibiotics administered in first 24 hours, measured for (1) all ED patients or (2) sepsis patients
- 3) Antibiotic overtreatment rate: Percentage of "sepsis mimic" patients who received IV or IVequivalent antibiotics in the ED.
- 4) New onset C. difficile colitis incidence: Percentage of (1) all ED patients and (2) ED sepsis patients with a positive stool test for *Clostridium difficile* colitis between 72 hours and 90 days after ED arrival.
- 5) Adverse drug & allergic reaction incidence: Measured as the fraction of 1) all ED patients and (2) ED sepsis patients with a discharge diagnosis code consistent with anaphylaxis or with an adverse reaction to antibiotics (see Appendix C).
- Potential exploratory outcomes
  - 1) Measures of organ failure trajectory, to include change in the SOFA score between hospital day 1 and hospital day 3, and overall and organ-specific measures of organ failure-free days through day 28.
    - Organ-failure free days (OFFD) are defined as the number of days from the time of the first SOFA score ≤1 above baseline to day 28 after ED arrival, assuming survival for at least two consecutive calendar days after the SOFA score ≤1 above baseline and continued SOFA score ≤1 point above baseline to day 28. If a patient has SOFA score rise again to ≥2 points above baseline and subsequently achieves SOFA score ≤1 point above baseline to day 28, VFDs will be counted from the end of the last period of SOFA score ≤1 to day 28. If a patient had SOFA score ≥2 points above baseline at day 27 or dies prior to day 28, OFFD will be zero
    - Support-free days (i.e. ventilator-free days) are calculated similar to OFFD
  - 2) Mortality at other intervals
  - 3) Testing and treatment utilization. Outcomes measured among (1) among all ED sepsis patients;
    (2) all ED patients; (3) "likely" sepsis patients
  - 4) Code Sepsis care process timing: measured among patients who received Code Sepsis protocol activation as time from protocol activation until completion of key protocol steps, to include blood culture collection, chest X-ray collection, team huddle, antibiotic initiation
  - 5) Timing of testing & care processes among all sepsis patients, to include ED clinician assessment, ED room placement, ED departure, blood culture collection, radiology testing, and order entry for antibiotics. Measured analogous to door-to-antibiotic time.
  - 6) Code Sepsis protocol adherence: measured as performance of protocol steps in correct order both individually and as a fraction of all possible.

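### Read literally, the relapse rule for organ-failure-free days (a potential exploratory outcome) gives zero days to patients who relapse and then recover, contradicting the rest of its own definition

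*Protocol*

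**What the plan says.** Protocol section 3.7.2 lists, under "Potential exploratory outcomes", the "overall and organ-specific measures of organ failure-free days through day 28". The definition has three parts.

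- **Base rule (no relapse).** OFFD is "defined as the number of days from the time of the first SOFA score ≤1 above baseline to day 28 after ED arrival", provided that the patient survives at least two further days and stays recovered.
- **Relapse rule.** It applies to a patient whose score rises again to at least 2 points above baseline and who "subsequently achieves SOFA score ≤1 point above baseline to day 28". For that patient, "VFDs will be counted from the end of the last period of SOFA score ≤1 to day 28".
- **Zero rule.** "If a patient had SOFA score ≥2 points above baseline at day 27 or dies prior to day 28, OFFD will be zero".

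The section then adds: "Support-free days (i.e. ventilator-free days) are calculated similar to OFFD".

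The SAP's tables of primary, secondary, safety and process outcomes contain no organ-failure-free, ventilator-free or support-free days. Nothing there restates or corrects the definition.

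**The concern.** The base rule starts the clock when recovery begins. The relapse rule starts it when the last recovered period ends. For the patients to whom the relapse rule applies, that period is still running on day 28, so no days are left to count.

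Two further slips in the same sentence point to a drafting error. It refers to VFDs while OFFD is being defined. It also drops the reference to baseline after the threshold of 1, although the rest of the definition is relative to baseline. For a patient whose baseline SOFA is 2 or more, an absolute score of 1 or less would mean a score below baseline.

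What is at stake is the scoring of one exploratory measure, and of any support-free-day measure built on it. Two programmers working from this sentence could derive different values for the same patient, and neither value would be sensible.

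**Working it through.** The documents contain no worked OFFD value, so there is no stated figure to reproduce. The check applies the written rule to assumed patient courses.

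**Inputs from protocol section 3.7.2:** a 28-day horizon; recovered means SOFA no more than 1 point above baseline; the three rules above. **Assumed:** one status per day, days 1 to 28, and the courses below, each with first recovery on day 5. **Formula:** OFFD = 28 − (day on which the count starts).

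**Step 1, no relapse.** The base rule gives 28 − 5 = 23.

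**Step 2, relapse on days 10-12.** The recovered periods are days 5-9 and days 13-28.

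- Literal: the last recovered period ends on day 28, so 28 − 28 = 0 (1 if day 28 itself counts).
- Pre-relapse reading: if the last period is taken as days 5-9, its end is day 9 and 28 − 9 = 19. Those 19 days are days 10-28, of which days 10-12 are organ failure. The score is therefore 3 relapse days plus 16 recovered days.
- Start of the last recovered period: 28 − 13 = 15.

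**Step 3, other courses.**

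| Course | Literal | Pre-relapse reading | Start of last recovered period | End of last failure period |
|---|---|---|---|---|
| Relapse days 10-12 | 0 | 28 − 9 = 19 | 28 − 13 = 15 | 28 − 12 = 16 |
| Relapse days 20-24 | 0 | 28 − 19 = 9 | 28 − 25 = 3 | 28 − 24 = 4 |
| Relapses days 8-9 and 15-17 | 0 | 28 − 14 = 14 | 28 − 18 = 10 | 28 − 17 = 11 |

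**Step 4, generality.** The literal zero does not depend on the course chosen. The rule applies only if recovery lasts to day 28, so the end of the last recovered period is always day 28. Enumerating every single-relapse course with first recovery on days 2 to 5 and the relapse over by day 26 gives 300 + 276 + 253 + 231 = 1,060 courses, and the literal score is 0 in all of them.

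**Step 5, against the zero rule.** None of these patients has organ failure at day 27 or dies before day 28. The zero rule therefore does not cover them, yet the literal relapse rule scores them as if it did.

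**Step 6, choice of anchor.** The last two columns of the table differ by one day throughout, purely from the day-boundary convention. The start of the last recovered period is the anchor that matches the base rule (Step 1).

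**The case against.** The strongest reply is that the intent is clear from context. The base rule counts from the start of recovery and the zero rule names who scores zero, so a careful programmer would see the slip. A reader might infer that relapsed survivors will be scored the same as patients who died. The documents do not support that as a prediction: it follows only if the sentence is coded literally, and the pre-relapse reading gives a different value, also wrong. What stands is that neither reading of the sentence as written gives a sensible score.

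A second reply is that no analysis specified in the SAP uses the measure. That is correct and limits the importance of the point. It does not remove the error, because the protocol keeps the measure as a possible outcome and no other text defines it.

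A reader might also want a cohort effect. At one assumed final recovery day (day 10, so 28 − 10 = 18 days lost), assumed shares of relapsed-then-recovered patients of 2%, 5% and 10% would lower the mean by 0.02 × 18 = 0.36, 0.05 × 18 = 0.9 and 0.10 × 18 = 1.8 days. The documents give neither the share nor the recovery day, so these figures are not estimates for this trial. The same scoring would also apply at every site in both phases. If the measure were analysed by difference-in-differences, the contrast would be biased only if the frequency or timing of relapse followed by recovery changed differently at the intervention and control sites.

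Finally, protocol section 9.2.3 says that follow-up after the hospital stay is limited to linked mortality data. Relapse after discharge would mostly go unseen, so the rule bears mainly on relapse and recovery within one stay. That stands, and it narrows the group affected.

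**Conclusion.** The relapse rule is wrong as written, and the consequence is minor. Read literally, it gives 0 days (1 if day 28 is counted) to every patient who relapses and then stays recovered to day 28, against both the base rule and the zero rule. Under the pre-relapse reading, it credits relapse days as failure-free. In the assumed course with relapse on days 10-12, the two readings give 0 and 19, against 15 from the start of the last recovered period.

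The conclusion about the wording rests on the text alone. The sizes rest on assumed courses with daily scores. The effect on the cohort mean is unknown. The carry-over to support-free days is a risk rather than a certainty, since the protocol says only that they are calculated similarly. A reader might infer that the trial's main results are exposed. They are not: the primary outcome, the secondary outcomes and the power calculation do not use this measure.

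**What to change.** Replace the relapse sentence in protocol section 3.7.2 with: *OFFDs will be counted to day 28 from the start of the last period with SOFA score ≤1 point above baseline.* This changes VFDs to OFFDs, changes the end of the period to its start, and restores the reference to baseline.

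Use this anchor only. Adding the end of the last failure period as an equivalent would bring back a one-day ambiguity on daily scores. The sponsor should confirm that this is the intended rule.

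State that support-free days use the same start-of-last-period rule. If OFFD is to be analysed, carry the corrected definition into the SAP.

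The cost is one sentence plus one clause. No new data are needed, and no other endpoint or analysis changes.
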